4.2.2 Recruitment

The primary recruitment for this study will be through participating NF Consortium Centers and orthopaedic centers. This prospective clinic trial will be posted on websites and included in the newsletters of the NF support organizations (CTF and NF Network). Directors and coordinators at each of the 42 clinics affiliated with the CTF NF Clinic Network will be notified of the trial and eligibility.

A total of between 36-52 patients will be enrolled prospectively in this trial. The maximum number of patients that will be enrolled in the BMP arm is 26, based on the numbers of Infuse kits supplied by the sponsor. The ideal number of Control patients is also 26, but may range from 10-26, based on preferences of enrollees. This is further discussed in the Study Modification section below, 4.2.3. We expect that dropout rate of participants, once they have been enrolled and had their surgical procedure performed, should be very low, in the range of 5%. The experience of participating surgeons is that their TPA patients who have had surgery are extremely likely to attend subsequent follow-up visits. The final endpoint of the trial is at the one-year assessment of the last patient enrolled. Due to slow enrollment in the first year of the trial, we have added 5 Shriners orthopedic centers in the U.S. as participants in the trial. Funding has been included to help support family travel as outlined, in the Informed Consent forms (range of \$200-\$500 per patient, with the greater amount for patients living further than 50 miles from the participating center). Participants who live further than 50 miles from a participating center may have an option to elect to have several of the follow-up visits and Xrays (3 and 9 months post-op) performed by their local orthopedic surgeon, with results sent to the DMAC and radiographic team at TSRH. However, the surgical procedure and follow-up visits at 6 and 12 months must be at a participating center with either the orthopaedic surgeon or the NF specialist. All centers performing any subject evaluations for the study must have completed the appropriate mandatory electronic training modules prior to performing any assessments.

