4.2.3 Enrollment procedures

The NF Clinical Trials Consortium will enroll subjects in this trial. Selected subjects with NF1 and tibial pseudarthrosis will be enrolled at the participating sites where surgery is anticipated. Personnel at the UAB NF Clinical Trials Consortium Operations Center will coordinate enrollment with the participating site, and ensure that eligibility requirements are met, prior to scheduling of surgery and shipment of rhBMP-2. As part of the consent process, patients and families will be provided information about the research aspect of this prospective clinical trial.

Study Modification: Enrollment: Patients may be enrolled on the study once all eligibility requirements for the study have been met. All patients/parents will discuss the study in detail with their surgeon, and will view a Powerpoint presentation about the study with a study coordinator present. **At the time of enrollment, parents/patients will be offered to choose either the Choice Arm or Randomized Arm of the study.** Those selecting the Choice Arm will be assigned to their treatment of choice (either BMP or Control). Those who choose the Randomized arm will be randomly assigned at a 2:3 ratio to BMP or Control group. It is

expected based on prior experience that more patients are likely to prefer the BMP arm. Therefore, the mildly unequal randomization of 2 BMP: 3 Controls is planned to improve the ability to achieve adequate controls for the study. For those in the Randomized arm, assignment will be accomplished by accessing a password controlled website maintained by the DMAC. The website is 21 CFR 11.10(d) compliant for FDA clinical trials.

That website will assign a new subject to a treatment group determined by a randomization list produced by the study statisticians employing a permuted block design. Randomization will be stratified by age (≤ 8 vs > 8 years) and prior surgery (Y/N). Enrollment and randomized treatment assignment must occur before the date of surgery but should be as close to the date of surgery as feasible.

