6.1 Statistics and Feasibility

The primary objective of this study is to determine if there is improved healing of tibia in patients treated with BMP-2, compared to those treated with standard surgical protocol alone. The primary outcome for the study will be radiographic evidence of tibial healing 12 months after surgery, using the RUST criteria as described in section 6.4. For each cortex a score of 1, 2, or 3 will be given. A non-visible cortex will be given a score of 1. The cortex scores will be added together for a total score. We will define three levels of healing: RUST score of 4-7, score 8-9, or score 10-12. The primary analysis will be to compare the distribution of scores across the 3 groups (4-7, 8-9, 10-12) at 12 months post-surgery using a Wilcoxon Test. The proportion of patients achieving **complete healing** (score 9-12, with at least 2 evaluable cortices having a score of 3) will also be calculated and an exact 95% confidence interval computed.

Analyses based on the actual 4 – 12 scores will also be performed and compared between the two groups. In addition, the % of patients having a **successful outcome** (defined as RUST score of 9 or greater, with at least 2 evaluable cortices having a score of 3) will be compared between the two groups. Time to union will be compared between the two groups based on Xrays obtained at 5 points after surgery (6 weeks, 3 mos, 6, 9, and 12 mos).

Subjects who experience a serious treatment-related adverse event, refracture, or need for reoperation will be considered to be **study failures**. The proportion of failures within each group will be compared to assess safety success.

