6.2 Power Analysis/Sample Size Justification

The primary study endpoint will be the subject's RUST score 12 months after surgery. The radiology panel determining RUST score will be blinded to the treatment status of all patients, whether in the Choice or Randomized arms. The two treatment groups will be compared with

respect to the RUST score using the Wilcoxon Rank Sum Test at the one sided 0.05 significance level.

Data from the TSRH of 12 patients treated without BMP but an identical surgical protocol showed RUST scores at 12 mos post surgery of: Score 4-7 in 33%; Score of 8-9 in 42%; and score of 10-12 in 25%. If the use of BMP improves these scores to: 15% 4-7; 20% 8-9, and 65% 10-12, as suggested by our data from [name] 16 patients treated with BMP, then it follows that for two patients randomly chosen, one from each treatment group, the probability that the patient in the BMP group will have a better score than the patient in the Control group is .691. Using a standard formula [Kolassa, 1995] implemented in nQuery Advisor® 7.0 this study with the initially planned sample size of 50 (25 per group) will have 86% power for a Wilcoxon Rank Sum Test at the one sided p.05 significance level.

Study Modification: Based on data from the first year of the trial, more eligible patients declined to participate than agreed to participate; however, in many of these cases the family would have agreed to a Parental Preference trial. Similar Parental Preference clinical trials have achieved acceptance within the orthopedic field, as demonstrated by the large BrAIST study of bracing versus no bracing for adolescent scoliosis [Weinstein et al, 2013; Schwieger et al., 2016]. The study was thus modified after initiation to allow a **Choice Group**, wherein after offering whether a potential participant had a preference, this would be honored. If there were no preference or if there is no option to obtain BMP at the institution where the participant is being seen, they would be **randomized** to BMP or Control using a 2:3 randomization. The rationale for this unbalanced randomization is to obtain or achieve enough controls to have a reasonable comparison of the effect of BMP. It is expected by participating surgeons that more patients would prefer the BMP arm to the Control arm if given the choice.

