We anticipate that this would leave the study with a potential slight imbalance in BMP treatment and controls. Thus, we evaluated the impact on the primary analysis given various scenarios on recruitment and testing treatment effects assuming the results of choice and randomized allocation could be pooled.

The study is limited by the company's allocation of just 26 BMP devices, so we examined the power of the study under various scenarios of BMP treated to Controls. The table below shows the power, along with the sample sizes (shown in italics in the table in the 4th and 5th rows), if the study ends up with 5 and 26 patients in Usual Care versus BMP, up to comparison of 20 Usual Care versus 26 BMP across the columns of the table. The power ranges from 46% power to detect a difference in RUST scores using a 1 tailed test at 0.05 to over 80% (as per our original primary analysis and endpoint). This is testing the RUST scores assuming UC of: 33% (Rust Scores 4-7), 42% (8-9) and 25% (10-12) compared to 15% (4-7); 20% (8-9) and 65% (10-12). So if we enroll at least 10 -15 controls, we have approaching 70% power to declare a significant difference. Obviously, we need to have a sufficient number of controls to enhance the power, and to help ensure this result, we will randomize 3 controls to 2 BMP cases in the randomization to enhance our ability to achieve at least 10 controls.

**Power using a Wilcoxon (Mann-Whitney) rank-sum test that $P(X < Y) = .5$ (ordered categories) (unequal n's), One sided Type I error=0.05
(Control Rust scores 33% (4-7), 42% (8-9), 25% (>=10) versus BMP 15%, 20%, 65% respectively)**

	1	2	3	4	5	6	7	8
Number of categories, k	3	3	3	3	3	3	3	3
$p_1 = P(X < Y)$	0.702	0.702	0.702	0.702	0.702	0.702	0.702	0.702
Power (%)	46	51	56	59	62	65	76	82

n_1	26	26	26	26	26	26	26	26
n_2	5	6	7	8	9	10	15	20

Our analysis will be a primary analysis combining the Choice and randomized participants. We will perform sensitivity analyses within the Choice and Randomized cohorts separately. Given the limited sample sizes, we do not expect significant differences, but will examine descriptive statistics comparing the Choice Group to the Randomized Group. We will examine the RUST scores amongst those who choose BMP versus those who refuse and choose usual care. We will of course, consider comparisons to historical controls should the results prove clearly different between the Choice and Randomized Groups.

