As we noted above, we expect that most of the data from this study will be generated by the choice arm and hope to maintain at least 10 randomized controls. We will compare the participant characteristics as well as Rust Scores between any controls identified by choice to those controls by randomization and more importantly RUST scores between the choice and randomized BMP treated arms. We will look at the overlap of the confidence intervals and test the equivalence of the two sets of results using two one sided tests of equivalence at the 5% level with an equivalence margin of 0.513. The margin of equivalence of 0.513 was derived based on the hypothesized difference between treatment and control originally planned and assuming these scores are normal continuous variables. Here we used the midpoint of each Rust Scoring Interval (5.5, 8.5 and 11) and computed the average Rust score for each group based on the hypothesized distribution in each group and ended up with a mean of 9.675 in the BMP group compared to 8.135 in the control group yielding an average difference in Rust Score of 1.54. We took 1/3 of the difference between the treatment average Rust score and the usual care Rust score ending up with an equivalence margin of 0.513. Since these sample sizes are small, we don't expect to reject the null hypothesis of differences as the power is probably low, but if they are different we understand that pooled results will be difficult to interpret. If these

tests of Choice versus Randomized treatment arms are not able to reject nonequivalence, we understand that this is not strong evidence for a lack of poolability between choice and randomization. Nevertheless, it will be sufficient to allow a comparison and calculation of the differences between the treatments and an overall assessment of the benefit of BMP in healing especially if we can demonstrate equivalence. Sensitivity analyses will be conducted using pooled and unpooled results as no statistical evidence of a lack of nonequivalence is not absolute evidence for nonequivalence.

Analyses:

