Since subjects, once they have had surgery, will need to be seen regularly for follow-up, we expect little or no attrition or loss to follow-up. Therefore, we will plan to enroll a total of between 36-52 patients, with a minimum goal of 15 eligible patients in the control arm and 26 patients in the BMP arm.

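### The primary BMP test pools self-selected and randomised patients without adjustment, omits the trial's own randomisation strata, and ties the planned cohort checks to no criterion

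*Combined protocol and SAP*

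**What the plan says.** **The test.** Section 6.2 fixes the analysis set: "Our analysis will be a primary analysis combining the Choice and randomized participants". Section 6.1 says the primary analysis will "compare the distribution of scores across the 3 groups (4-7, 8-9, 10-12) at 12 months post-surgery using a Wilcoxon Test", and section 6.2 compares the groups with "respect to the RUST score using the Wilcoxon Rank Sum Test at the one sided 0.05 significance level". Neither section names a covariate, stratum or weight.

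**Allocation.** Under section 4.2.3, Choice patients receive the treatment their family prefers. The others are randomised 2 BMP to 3 control, stratified by age (8 or under, over 8) and prior surgery. Participating surgeons expect that "more patients would prefer the BMP arm to the Control arm if given the choice". Section 4.2.2 caps BMP at 26 patients; the number of controls "may range from 10-26, based on preferences of enrollees". Section 6.2 sets total enrolment at 36 to 52, "with a minimum goal of 15 eligible patients in the control arm and 26 patients in the BMP arm". Under Generalizability of the Results, the authors expect that "most of the data from this study will be generated by the choice arm and hope to maintain at least 10 randomized controls".

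**Age and prior surgery.** In section 6.2 they appear as imputation variables (Missing data) and as factors compared within each treatment group (Analyses). They do not appear in the comparison of BMP with control.

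**Cohort checks.** Section 6.2 plans separate Choice and Randomized analyses, pooled and unpooled sensitivity analyses, descriptive comparisons, and two one-sided equivalence tests with margin 0.513. It concedes low power for the equivalence tests, accepts that pooled results would be hard to interpret if the cohorts differ, and would consider historical controls in that event. Sections 4.2.3 and 6.2 keep the radiograph panel blinded for all patients.

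**The concern.** An unadjusted test on the combined set is protected by randomisation only for the randomised part. If families who choose tend to choose BMP, and randomised patients tend to receive control, then the comparison of BMP with control is partly a comparison of Choice with Randomized patients. Prognosis may also differ between those who choose BMP and those who choose control. Either difference moves the primary p-value.

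The two baseline factors that the trial thought important enough to stratify on are balanced by design only among randomised patients, whom the plan expects to be the minority. Leaving them out of the test gives up protection that is available from data already collected.

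If the pooled p-value is below 0.05 and the checks disagree with it, the plan does not say what will be concluded. Section 4.1 expects the result to influence surgical decisions, and section 3.9 would use the better arm as a future control arm.

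**Working it through.** **1. The plan's own power figure (section 6.2 table).** With control 33/42/25% and BMP 15/20/65%:
- p1 = 0.33×(0.20+0.65) + 0.42×0.65 + 0.5×(0.33×0.15 + 0.42×0.20 + 0.25×0.65) = 0.5535 + 0.148 = 0.7015 (stated 0.702).
- Tie-corrected null variance: V0 = (N+1)(1−Σt³)/(12·n1·n2). For 26 v 10 the pooled shares t are 0.200, 0.261 and 0.539, so V0 = 37×0.8177/3120 = 0.00970.
- Power = Φ(0.2015/0.0985 − 1.645) = 65.6% (stated 65%). For 26 v 15 it is 75.0% (stated 76%).

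All eight table entries reproduce within 2 points. The table assumes that the cohorts can be pooled.

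**2. A cohort split.** The documents give targets, not a split. One reading is 26 BMP and 15 controls, 10 of the controls randomised, with 2:3 allocation. Randomised BMP is 10×2/3, about 7. Choice is then 26−7 = 19 BMP and 15−10 = 5 controls. The BMP share is 19/24 = 79% in Choice and 7/17 = 41% in Randomized.

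**3. Type I error with no BMP effect.** Randomized patients follow 33/42/25%. In Choice, the odds of exceeding each cut are multiplied by an assumed odds ratio (OR). At OR 2, for example, P(10–12) has odds (0.25/0.75)×2 = 0.667, which is 40%. Simulation at 19:5 (Choice) + 7:10 (Randomized):

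| Choice v Randomized OR | 0.5 | 1 | 1.5 | 2 | 3 |
|---|---|---|---|---|---|
| Pooled test, % | 1.7 | 5.0 | 8.3 | 11.2 | 15.9 |
| Stratified by cohort, % | about 5 | about 5 | about 5 | about 5 | about 5 |

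The split matters. At OR 2 the pooled error is about 8.5–9.5% for 16:10 + 10:15 or 17:5 + 9:10. It is about 18% for 19:0 + 7:10, which is the 26 v 10 minimum with every control randomised.

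**4. Power at the planned effect, 19:5 + 7:10.** Pooled power is 77% with no cohort difference. If Choice patients do worse (OR 0.5) it falls to 56%, against 67% stratified by cohort.

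**5. Selection within Choice.** If only BMP choosers have better prognosis (OR 2), type I error is about 20.5% pooled and 12.8% stratified by cohort. The randomised-only test stays near 5%.

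**6. Imbalance in the strata.** Assume prior surgery in 30% of BMP v 40% of control patients with OR 0.6, up to 20% v 50% with OR 0.4, and age OR 0.5. The unadjusted error is 5.7–11.2%. Least squares on midranks with age and prior surgery as covariates (rank-ANCOVA) gives 4.8–5.0%. These cases all favour BMP; imbalance the other way would make the unadjusted test conservative.

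**7. The equivalence test.** The plan's midpoints (5.5, 8.5, 11) give means 9.675 and 8.135, and (9.675−8.135)/3 = 0.513, as stated. They imply SDs of 2.01 (BMP) and 2.10 (control). Half-widths of the 90% CI are:
- BMP, 19 v 7: 1.711×2.01×√(1/19+1/7) = 1.52.
- Control, 5 v 10: 1.771×2.10×√(1/5+1/10) = 2.04.

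Both are about 3 to 4 times the margin, so equivalence cannot be concluded at these SDs whatever difference is observed. Simulated power was 0.0% in every split tried.

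**The case against.** **The plan already deals with selection.** In part it does. It prespecifies separate and pooled analyses, admits that differing cohorts would make the pooled result hard to interpret, and mentions historical controls. A reader might infer that the checks have no role at all; the text does not support that. What is missing is a criterion. The plan also says that failing to show equivalence is not strong evidence against pooling, and that an overall assessment of BMP will be made.

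**Blinded reading protects the endpoint.** It removes assessment bias. It does not affect who chose which treatment.

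**The sizes are assumed.** This stands. The documents give no odds ratio for cohort, choice, age or prior surgery. The 19:5 + 7:10 split combines a minimum goal with a hope. It also applies 2:3 to every randomised patient, although the first year preceded the modification and 25 per group was then planned. A reader might infer that the pooled test is known to be inflated in favour of BMP. The documents do not support that: the direction is unknown, and at OR 0.5 the test is conservative.

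**Adjusting for age and prior surgery does not address pooling.** This also stands. If a cohort effect is unrelated to those factors, the adjusted primary test still has about 11% error at OR 2. Making cohort adjustment primary would cost substantial power, which is why it is proposed as support.

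**Conclusion.** The concern holds and should be fixed before unblinding. The firm part is structural. The primary test is unadjusted, its two cohorts are expected to differ in BMP share, the randomisation strata are absent from it, and no planned check has a binding criterion. The failure of the equivalence test is also firm, given the SDs implied by the plan's own midpoints.

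The size is illustrative. For assumed cohort ORs from 0.5 to 3 at 19:5 + 7:10, type I error runs from 1.7% to 15.9% against a nominal 5%; other splits give less or more. The plan's power arithmetic is sound under its pooling assumption, so nothing here shows that the power table is wrong or that pooling must be abandoned.

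**What to change.** 1. **Primary test.** Use a one-sided rank-ANCOVA, or an equivalent stratified rank test, of the same three-level 12-month RUST outcome on the combined set, adjusted for age (≤8, >8) and prior surgery. Name the same model in the imputation step. State that this protects only against imbalance in those two factors and does not remove a cohort effect. At 19:5 + 7:10, power is 75.6% v 76.8% unadjusted if neither factor is prognostic, and 77.5% v 76.9% if both are (OR 0.5 each). At 20:2 + 6:9, the non-prognostic case is 68.3% v 70.5%. The cost is about 1 to 2 points at most.
2. **Supporting results.** Prespecify an analysis that adds cohort, and report the already planned randomised-only estimate with its CI beside the primary result. State their lower power. Cohort-adjusted power is about 71% v 77% at 19:5 + 7:10, and about 46–50% v 68% at 26 v 10 if all 10 controls are randomised. The randomised-only test has about 46% power at 7 v 10.
3. **Wording.** State before unblinding that if these results do not support the primary one, it is reported as an association and not as an effect of BMP. A numerical cut is optional, for example a cohort-adjusted one-sided p below 0.10 with the randomised-only estimate favouring BMP. At 19:5 + 7:10 it cuts false claims at cohort OR 2 from 11.2% to 7.6%, and the chance of a claim under the planned effect from 77% to about 74%. At 26 v 10 that chance falls from 68% to about 53–56%, so the cut is a trade-off for the sponsor to decide.
4. **Equivalence test.** Do not use the 0.513 test as evidence on poolability.
5. **Limit.** State that no adjustment removes unmeasured selection within Choice.

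All of this is SAP wording on variables already collected.

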As noted above we are likely giving up some power with this change to a Choice Design. Our assumption based on the current rate of declining to participate is that more patients will chose the BMP arm above the Control arm, but if we are incorrect, we would have adequate power (76% - 82%) if we were able to enroll 15-20 patients in the Control arm and 26 patients in the BMP arm. Even in a worse scenario that we were only able to recruit 10 patients to the Control arm + 26 to BMP, we would still have reasonable power of 65% to show a difference between the groups.

It is important to note that, although participants and providers in the Choice Arm will no longer be blinded to the treatment status of the participants, the Primary Outcome Measure (RUST score), will be determined by a group of 4 radiologists, all blinded to the treatment status of all participants.

Missing data: Reason for any missing 12 month radiographic data will be recorded by treatment group. Data from subjects missing the 12 month radiograph will not be included, unless multiple imputation is applied. Although minimal data are expected to be missing, multiple imputation technique will be used if 5% or more data are missing. This multiple imputation will replace the missing value with a set of plausible values that represent the uncertainty about the right value to impute. The multiply imputed data sets will then be analyzed by using the Wilcoxon Rank Sum Test for complete data on each and combining the results from these analyses. The variables used for the imputation will be RUST score at 6 months, age, prior surgery (Yes=1, No=0), and timed 10 meter walk at 12 months post-surgery.

Generalizability of the Results:

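### The primary analysis drops patients without a 12-month film unless an undefined 5% of data are missing; one imputation method should apply to any missing 12-month RUST score

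*Combined protocol and SAP*

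**What the plan says.** Section 6.2 (Missing data) sets two rules for the primary endpoint. The first is the default: "Data from subjects missing the 12 month radiograph will not be included, unless multiple imputation is applied". The second is the exception: "multiple imputation technique will be used if 5% or more data are missing". It does not say whether the 5% is counted over all patients, within each arm or per variable. The imputation predictors listed there are the 6-month RUST score, age, previous surgery and the 12-month timed walk. Treatment group is not among them.

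The primary test compares the groups with "respect to the RUST score using the Wilcoxon Rank Sum Test at the one sided 0.05 significance level".

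On size, section 4.2.2 says "A total of between 36-52 patients will be enrolled prospectively in this trial" and that the number of controls "may range from 10-26, based on preferences of enrollees". The close of section 6.2 restates the total "with a minimum goal of 15 eligible patients in the control arm and 26 patients in the BMP arm".

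On attrition, section 4.2.2 says dropout after surgery "should be very low, in the range of 5" percent. The close of section 6.2 expects almost none.

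Section 6.2 (Analyses) bases all analyses on evaluable patients and adds a sensitivity analysis that counts inevaluable patients as failures (scores 4-7). For the definition of evaluable it points to a section 10.5, but the document's numbered sections end at 6.6.

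**The concern.** The number of missing films decides which primary analysis is run, and the trigger sits at the loss rate the plan expects. One patient more or less can change the method.

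The control arm may be as small as 10 to 15. A percentage that looks small over the whole sample can therefore be a sizeable share of the controls. Below the trigger those patients are removed, even if they have RUST scores from earlier visits that carry information about healing.

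Loss related to healing is possible under this protocol. Section 5.9 removes patients for not complying with cast or brace, or for missing more than two visits. Families in the Choice Arm know the treatment, so loss could also differ between arms. If it does, the complete-case comparison is biased.

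**Working it through.** **Inputs.** Category rates from the power table in section 6.2: "Control Rust scores 33% (4-7), 42% (8-9), 25% (>=10) versus BMP 15%, 20%, 65% respectively". One-sided 0.05 Wilcoxon test. 26 BMP patients with 10 to 26 controls. Trigger 5%. Dropout 5% (section 4.2.2), with 2% and 10% as assumed alternatives.

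**Step 1: reproduce the plan's power (26 v 15, stated 76%).**
- Probability that a BMP patient scores better, counting ties as half: 0.33 × (0.85 + 0.075) + 0.42 × (0.65 + 0.10) + 0.25 × 0.325 = 0.7015. The plan has 0.702.
- Tie-corrected null variance: (N + 1)/(12 × n1 × n2) × (1 − Σt³), where t are the pooled category rates. With N = 41 and t = 0.216, 0.280, 0.504 this is 42/4680 × 0.840 = 0.00754, so SE = 0.0868.
- Power = Φ(0.2015/0.0868 − 1.645) = 75.0%. With separate null and alternative variances it is 77.2%. All eight entries of the plan's table reproduce within 2 points.

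**Step 2: how many can be dropped unimputed (pooled reading).** This is the largest m with m/N < 5%.
- N = 36 to 40: m = 1. At 26 v 10, 1/36 = 2.8% overall but 1/10 = 10% of controls.
- N = 41 to 52: m = 2. At 26 v 15, 2/41 = 4.9% overall but 2/15 = 13.3% of controls. This is the maximum over the allowed arm sizes.
- Both must be controls. If 2 of 41 are lost at random, that has probability C(15,2)/C(41,2) = 105/820 = 12.8%.

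**Step 3: chance that imputation is triggered**, P(Binomial(N, d) ≥ m + 1) for dropout d.

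| N | d = 2% | d = 5% | d = 10% |
|---|---|---|---|
| 36 | 16% | 54% | 89% |
| 40 | 19% | 60% | 92% |
| 41 | 5% | 34% | 79% |
| 46 | 6% | 41% | 85% |
| 52 | 9% | 49% | 90% |

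**Step 4: effect of the loss itself** (simulation, tie-corrected Wilcoxon). In the informative case every lost patient is in one arm and would have scored 4-7. For power the lost patients are controls. For type I error they are BMP patients, with no true effect.

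| BMP v control, number lost | Power, all films | Power, random loss | Power, informative | Type I error, informative |
|---|---|---|---|---|
| 26 v 10, 1 | 68% | 66% | 56% | 7% |
| 26 v 15, 2 | 77% | 74% | 60% | 10% |
| 26 v 26, 2 | 87% | 86% | 79% | 11% |

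With random loss, type I error stays at 5%.

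**Step 5: would imputation help?** It depends on what the model knows.
- *No informative covariate*, same informative loss as step 4, complete-case against imputation within arm: power 57% v 57% (26 v 10), 60% v 62% (26 v 15), 79% v 80% (26 v 26). With treatment left out of the model, imputation gives 52%, 56% and 78%. Type I error stays at about 7%, 9-10% and 10-11%.
- *6-month RUST informative.* Assume a 6- to 12-month correlation of 0.5 to 0.85 and loss of the two patients in one arm who were worst at 6 months (26 v 15). Power is 61-66% complete-case against about 75% imputed (77% with all films). Type I error is 7.5-9% against 5-6%.

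The documents give no such correlation, so the second result is conditional on that range.

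**The case against.** The strongest reply is that the large losses in step 4 are not caused by the 5% switch. They compare informative loss with having every film, and where loss depends on the unseen 12-month outcome, removing a threshold does not cure it. This stands. A reader might infer that the switch costs 17 points of power or doubles the type I error; the documents and the calculations do not support that.

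A reader might also take it that the plan counts the 5% over the whole sample. That is the natural reading, but the text gives no denominator. Under a per-arm trigger, 1 of 15 (6.7%) or 1 of 10 (10%) would already start imputation, and the 13% could not occur.

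Nor is the choice of method simply a coin toss. The 13% arises only at N = 41, where the trigger probability at 5% dropout is 34%. If attrition is as low as the close of section 6.2 expects, imputation is seldom triggered, and complete-case analysis becomes the usual result.

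The informative scenario is extreme. At 26 v 15, two random losses that are both controls and both in the lowest class have probability of about 0.128 × 0.33² = 1.4%. Section 4.2.2 reports surgeons' experience that these patients keep their follow-up visits.

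Finally, the rule is pre-specified, and the failure-coded sensitivity analysis would expose the problem. Both are true. But that analysis leaves the primary result and the count-dependent choice of method as they are.

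**Conclusion.** The concern holds in a limited form. The primary method depends on a missing-data count with no defined denominator, at a threshold equal to the expected dropout. On the pooled reading, up to 1 of 10 or 2 of 15 controls can be discarded although their 6-month RUST may be on file.

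If loss is unrelated to healing, little is at stake: 1 to 3 points of power and no change in type I error. If loss is related to healing, the primary result can shift materially. Imputation then protects it only to the extent that earlier RUST scores explain who is missing and treatment is in the model. The imputation model as listed omits treatment and uses the 12-month walk, which is likely to be missing in the same patients. Deleting the threshold without correcting the model would therefore not be enough.

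**What to change.** In section 6.2 (Missing data):
- Delete the 5% condition and make multiple imputation the single primary method for any missing 12-month RUST score.
- Include treatment group and the earlier RUST scores (6 and 9 months) in the imputation model, and do not rely on the 12-month timed walk.
- Keep the complete-case analysis and the failure-coded (4-7) analysis as sensitivity analyses.

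The reference to section 10.5 should be replaced by a definition of evaluable that fits this rule.

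The cost is a wording change, a little extra analysis and some model dependence when only one or two films are missing. Enrolment, visits and patient care are unaffected. The change should be made before treatment-group results are seen.
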